8. DATA MANAGEMENT

- For this study, subject data will be entered into GSK defined CRFs, transmitted electronically to GSK or designee and combined with data provided from other sources in a validated data system.
- Management of clinical data will be performed in accordance with applicable GSK standards and data cleaning procedures to ensure the integrity of the data, e.g., removing errors and inconsistencies in the data.
- Adverse events and concomitant medications terms will be coded using MedDRA (Medical Dictionary for Regulatory Activities) and an internal validated medication dictionary, GSKDrug.
- CRFs (including queries and audit trails) will be retained by GSK, and copies will be sent to the investigator to maintain as the investigator copy. Subject initials will not be collected or transmitted to GSK according to GSK policy.

9. STATISTICAL CONSIDERATIONS AND DATA ANALYSES

9.1. Hypotheses

No formal hypothesis testing is planned. The primary objective of this study is to characterize the clinical activity of mepolizumab. A Bayesian approach will be employed to estimate the posterior probability that 1) the IGA response rate for mepolizumab is 40% or greater, and 2) that the improvement over placebo in IGA response rate is at least 15 percentage points.

Descriptive statistics including point estimates and corresponding 90% confidence/credible intervals will be provided for efficacy endpoints.

9.2. Sample Size Considerations

9.2.1. Sample Size Assumptions

The primary endpoint will be the proportion of subjects who achieve treatment success defined as an IGA score of 0 or 1 and at least a 2-grade improvement at Week 16.

Sample size is based on the objective to characterize the clinical activity of mepolizumab in subjects with moderate-to-severe atopic dermatitis. In order to characterize this, we assume that a 40% IGA response rate in the mepolizumab group and a 10% IGA response in the placebo arm, as well as an at least 15 percentage point improvement over placebo, will constitute a clinically meaningful improvement.

Using Bayesian posterior probability and assuming a flat large variance normal prior for difference in response rate, 25 mepolizumab subjects and 25 placebo subjects (single formal interim at 50% of subjects) will power the study to approximately 80% with predictive probability method based on the success criteria that $P(\text{difference in response rate} \geq 15\% | \text{Data})$ greater than 70% if the true response rate is 40% for mepolizumab group and 10% for placebo group. The 80% credible intervals for the difference in response rate will be presented. No pairwise comparisons are planned.

The primary analysis will be performed on the Intent-to-Treat (ITT) population, with a supporting analysis of the per protocol (PP) population.

9.2.2. Sample Size Sensitivity

If either the actual percentage of patients on placebo that achieve an IGA score of 0 or 1 at Week 16 and at least a 2-grade improvement or the treatment effect of mepolizumab is different from the values assumed in Section 9.2.1, the power to detect a change in the proportion of subjects that achieve an IGA score of 0 or 1 and at least a 2-grade improvement at Week 16 will be affected.

Table 7 Sample Size Effects on the Predictive Probability of Success at the End of the Study

Prior used	Total Sample Size	Probability of Success
Consensus prior	40	0.745
	50	0.799
	60	0.833
	70	0.866

9.2.3. Sample Size Re-estimation or Adjustment

No sample size adjustment is planned.

9.3. Data Analysis Considerations

All pre-specified analyses will be described in a full RAP which will be finalized prior to unblinding. The study will be unblinded once the final subject has completed the Week 20 visit, all queries for data collected up to this time are resolved, and the clinical study database is frozen.

9.3.1. Analysis Populations

Intent-to-Treat Population:

The intent-to-treat (ITT) population will consist of all subjects who are randomized and who received at least one dose of trial medication. Randomized subjects will be assumed to have received study treatment unless definitive evidence to the contrary exists. This will constitute the primary population for all analyses of efficacy measures.

Per Protocol Population:

The Per Protocol (PP) population will consist of all subjects in the Intent-to-Treat population not identified as full protocol deviators with respect to criteria that are considered to impact the primary efficacy analysis. The decision to exclude a subject from the PP population or exclude part of their data from the PP population analyses will be made prior to breaking the blind. The PP population will be used for a supplementary analysis of the primary endpoint. The PP population will not be analyzed if this population comprises more than 95% or less than 50% of the ITT population.

Safety Population:

All subjects who received at least one dose of a study treatment will be included in the safety population. Data will be summarized by actual treatment received. This population will be used in the evaluation of safety and tolerability.

PK Population:

The PK population is defined as all subjects in the ITT population who received at least one dose of study medication and for whom at least a PK sample was obtained, analyzed and was measurable. This will be the primary population for assessing PK.

PD Population:

The PD population is defined as all subjects in the ITT population who received at least one dose of study treatment and who also have a baseline serum PD measurement and at least one post-treatment serum PD measurement. This will be the primary population for assessing PD.

Biopsy Population:

The Biopsy population is defined as all subjects in the ITT population who have a baseline measurement and who also have at least one post-treatment PD biomarker measurement derived from skin biopsy samples. This will be the population used for the biopsy sub-study.

9.3.2. Administrative Interim Analyses

- Unblinded in-stream study data summaries will be generated by a GSK study statistician and study programmer. The unblinded summaries will be provided to GSK senior manager(s) for their review of subject efficacy and safety data. These results and randomization assignments will only be shared with members involved in the review and conduct of the analysis.

9.3.3. Formal Interim Analysis

A formal interim analysis may be performed after approximately 50% of subjects have been randomized and have had the opportunity to complete the Week 8 visit for futility and to enable future planning. If the study is anticipated to be fully enrolled at the projected time for this analysis, the interim may not be conducted.

It is expected that GSK's study statistician, programmer, clinical scientist, project physician lead, and/or respective designee(s) will be responsible for presenting the unblinded formal interim analyses. To do so, they will be unblinded to subject level data for the subjects enrolled in the study at the time the database is locked for the purpose of the interim analyses. These persons will not share subject-level randomization assignments with anyone not involved in conducting the analyses. The protection of the study blind and the dissemination plan for summary level results of the interim analyses will be described in the RAP.

The formal interim analyses will include an assessment of the proportion of subjects who have an IGA score of 0 or 1 and a minimum 2-grade improvement from baseline at Week 8 and later time points, and assessments of key secondary endpoints (e.g., change from baseline for EASI score) and key safety data. The interim analysis will not be used to declare success. Futility will be evaluated and may be declared if the predictive probability of meeting the assumptions in Section 9.2.1 is less than 10%.

A full database cleaning is not required for the interim analysis.

9.4. Key Elements of Analysis Plan

9.4.1. Primary Analyses

The primary efficacy endpoint is the IGA response rate at week 16. The observed response rate and difference between mepolizumab and placebo and the 80% credible interval for the response rate and the difference in response rate will be presented. The posterior probability that the IGA response rate for mepolizumab is 40% or greater and that the improvement over placebo is at least 15 percentage points will be calculated.

Subjects withdrawing prematurely from the study prior to the Week 16 visit will be assumed to be non-responders.

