- Subjects who are withdrawn from the study will complete an Early Withdrawal visit and then exit the study. See Section 5.4 and Table 3.

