This study will investigate the efficacy of mepolizumab at a SC dose of 100 mg administered every 4 weeks in subjects with moderate to severe AD. Subjects with mild AD will be excluded because they can be adequately treated with topical therapies. Published data have indicated elevated blood eosinophil counts in patients with moderate to severe AD [Trempe, 2011; Hon, 2007; La Grutta, 2005; Yoshida, 2002]. An inclusion criterion of blood eosinophils ≥ 350 cells/ μL has been selected based on data from Study SB240563/045 where approximately 70% of subjects had a baseline blood eosinophil count above this threshold. This inclusion criterion has therefore been selected to ensure the enrollment of subjects with meaningfully high blood eosinophil counts. The relationship between baseline blood eosinophil count and efficacy will be explored in this

study. In addition, the value of baseline biomarkers (ECP, IgE, and levels of chemokines such as TARC) as predictors of response will be evaluated.

The use of a non-prescription, non-medicated (without an active ingredient) emollient is required twice daily for the 7 consecutive days preceding the Baseline visit. Subjects whose disease is adequately managed by the non-prescription, non-medicated emollient during this 7-day period will not be eligible for the study. The requirement for the continued use of the concurrent non-prescription, non-medicated emollient throughout the remainder of the study ensures a consistent standard of care treatment for all subjects. Examples of acceptable emollients will be supplied in the SRM. The subject will use the same emollient throughout the study to ensure consistency. If the investigator determines it is in the best interest of the subject to initiate treatment with a prohibited medication or therapy, study treatment will be discontinued (if applicable), and the procedures and visits described in Section 5.4 and Table 3 will be performed.

The study will be conducted at multiple study centers to increase the generalizability of the study results.

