5.4.1. Early Withdrawal from Study Treatment

Subjects must **permanently discontinue study treatment** for any of the following reasons:

- Subject presents with worsening AD or any other condition that requires treatment with a prohibited medication.
- Subject experiences an adverse event(s) which is considered to be related to study treatment or study procedures and, in the investigator's judgment, is severe enough in nature to warrant treatment discontinuation.
- Subject experiences a cardiovascular or hematologic AE consistent with specific Common Terminology Criteria for AEs (CTCAE) version 4.02 Grade 2 (moderate) or higher (See SRM).
- The subject's randomized treatment assignment is unblinded by the investigator or treating physician.
- Subject becomes pregnant.
- Sponsor request (after discussion with the investigator), for reasons such as a significant protocol deviations or subject noncompliance.
- Study is terminated by the sponsor.
- Subject meets liver chemistry stopping criteria (See Section 5.4.4).
- Subject meets QTcF stopping criteria (See Section 5.4.5).

Subjects who permanently discontinue study treatment will be followed for 8 weeks after the last dose of study treatment. Every effort will be made by the investigator to encourage the subject to remain in the study to complete the two Post-Treatment visits providing that consent has not been withdrawn for subsequent visits.

If the decision is made to permanently discontinue study treatment less than 4 weeks after the last dose, an Early Withdrawal Visit will be scheduled as soon as is reasonably possible. Post-Treatment Visit 1 will then be scheduled 4 weeks after the last dose of study treatment, and Post-Treatment Visit 2 will be scheduled 8 weeks after the last dose of study treatment.

If the decision is made to permanently discontinue study treatment at a scheduled visit and approximately 4 weeks have elapsed since the last dose of study treatment, the procedures of Post-Treatment Visit 1 will be performed. Post-Treatment Visit 2 will be scheduled 8 weeks following the last dose of study treatment.

The investigator will record the primary reason for permanent discontinuation of study treatment and subsequent study withdrawal in the electronic Case Report Form (eCRF).

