5.5. Subject and Study Completion

A subject will be considered to have **completed study treatment** if he/she receives all planned doses of study treatment through Week 12 and completes the Week 16 visit (final primary endpoint visit). A subject will be considered to have **completed the study** if he/she receives all planned doses of study treatment and completes the Week 16 (Post-Treatment 1) and Week 20 (Post-Treatment 2) visits.

The end of the study is defined as the last subject's last visit.

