6.10.2. Prohibited Medications and Non-Drug Therapies

The prohibited concomitant medications and non-drug therapies listed in Table 1 will not be used from the specified period before the Screening visit and thereafter for the duration of the study except as stated below.

After completing the Week 16 visit, or after Early Withdrawal from Treatment, subjects may use prohibited concomitant medications for the treatment of worsening AD. The use of topical therapies after the Week 16 or Early Withdrawal visit is preferred. The use of systemic therapies during this time is at the investigator's discretion.

The subject must permanently discontinue study treatment if the subject presents with worsening AD or any other condition that requires treatment with a prohibited medication prior to administration of the Week 12 dose of study treatment, and the procedures described in Section 5.4 and Table 3 will apply. If the subject takes a prohibited medication or uses a non-drug therapy for reasons other than worsening AD, the investigator should consult with the medical monitor to determine if the subject should be withdrawn from study treatment and/or the study.

Table 1 Prohibited Concomitant Medications and Non-Drug Therapies

Prohibited Medication or Non-Drug Therapy (Note: Examples are not all-inclusive.)	Prohibited period before the Screening visit
Allergen immunotherapy (desensitization therapy)	6 months
Biologic agents	12 weeks or 5 half-lives, whichever is longer (e.g., 18 weeks for omalizumab)
Other investigational products	30 days, 5 half-lives or twice the duration of the biological effect of the investigational product (whichever is longer)
Oral or systemic glucocorticoids (e.g., hydrocortisone, cortisol, prednisone, prednisolone, methylprednisolone, dexamethasone, betamethasone, etc.)	4 weeks
Oral or systemic cytotoxic antibiotics (e.g., actinomycin, bleomycin, plicamycin, mitomycin, etc.)	4 weeks
Oral or systemic antimetabolites (e.g., methotrexate, azathioprine, mercaptopurine, etc.)	4 weeks
Oral or systemic alkylating agents (e.g., mechlorethamine, cyclophosphamide, melphalan, chlorambucil, ifosfamide, busulfan, etc.)	4 weeks
Mycophenolate: mycophenolate mofetil	4 weeks
Oral or systemic drugs acting on immunophilins (e.g., oral calcineurin inhibitors, cyclosporin, etc.)	4 weeks
Interferon-gamma	4 weeks
Adrenocorticotrophic hormone analogs	4 weeks
Phototherapy (See Section 6.9 for tanning booth/parlor restrictions.)	4 weeks
Coal tar	4 weeks

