12.2. Appendix 2: Assessment Windows

Clinic visits are scheduled to take place as specified in the protocol. Unscheduled visit will be excluded from analyses on any population. For all clinic visits, nominal visit days and times will be used for reporting; for example, if a subject recorded value on the Week 4 visit that were made on Week 3 of treatment, they will be presented as Week 4 values.

If a subject withdraws at a scheduled visit, and these data were scheduled to be collected at that visit, the data will be summarised and analysed (as appropriate) together with data from subjects who did not withdraw. If a subject withdraws at a scheduled visit at which these data were not scheduled to be collected, or if a subject withdraws between scheduled visits, data will be slotted to the next visit where the data was scheduled to be collected according to the study flowchart. The protocol visits windows of ± 3 days should be applied to the assignment of withdrawal visits, so that if a subject withdraws within the appropriate number of days from the last visit where that data was scheduled to be collected, they would get that data slotted to that visit and otherwise the data will be slotted to the next scheduled visit.

The early withdrawal visit will then be re-labelled as the corresponding visit. The same approach will be followed to Post Treatment 1 and Post Treatment 2 visits.

If there is more than one assessment associated with a particular visit interval, then the latest assessment will be used for summary tables and analyses. Where two or more findings (e.g. ECG (i.e. site interpretations will be used), laboratory data) slot to the same visit interval, the most 'abnormal' results will be used, i.e. according to the following hierarchy: Abnormal-Clinically Significant > Abnormal – not clinically significant > Normal.

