12.5.3. Efficacy

Efficacy
Investigators Global Assessment (IGA)

CCI - This section contained Clinical Outcome Assessment data collection questionnaires or indices, which are protected by third party copyright laws and therefore have been excluded.

 A Responder is defined as a subject who has an IGA score of 0 or 1 and a minimum 2-grade improvement from baseline. This is calculated for each study visit. As per protocol, a non-responder imputation will be used for all early withdrawal subjects where

Efficacy

subject's data will be imputed as a Non-Responder for all post withdrawal visits. This imputation will be used for summary and analysis table for primary and secondary endpoints.

- The observed IGA score classifications will be used for each visit. For all early withdrawal subjects the data from Post-Treatment 1/Post-Treatment 2/Early Withdrawal visits will be slotted using the algorithm detailed in Section 12.2
- AD flare/relapse for IGA is defined as IGA score of 3 or 4 after achieving an IGA score of 0 or 1 and at least a 2- grade improvement from the baseline.

Body Surface Area

Body Region	% Involvement (0-100% each area)	% Involvement x Proportionality Multiplier	Regional % BSA Involvement
Head and neck		___ x 0.1	
Upper extremities		___ x 0.2	
Trunk		___ x 0.3	
Lower extremities		___ x 0.4	
Total Involved % BSA (sum of the 4 area values) =			_____

EASI

CCI - This section contained Clinical Outcome Assessment data collection questionnaires or indices, which are protected by third party copyright laws and therefore have been excluded.

- The observed EASI data will be used for each visit. For all early withdrawal subjects, data from Post-Treatment 1/Post-Treatment 2/ Early Withdrawal visits will be slotted using the algorithm detailed in Section 12.2.
- AD flare/relapse for EASI is defined as increase in EASI score of ≥25% from Baseline.

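### The plan has no explicit rule scoring prohibited AD therapy before Week 16 as non-response; the IGA wording conflicts, and EASI-50/75 can count post-rescue scores as responses

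*Protocol*

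**What the plan says.** Protocol 4.2.1 explains that the Table 1 therapies are barred so that mepolizumab can be evaluated as the only AD treatment. Several sections then govern what happens when one is used.

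- **Stopping treatment.** Protocol 4.2.4 and 5.4.1 require permanent withdrawal from study treatment when worsening AD needs a prohibited medication. Neither sets a Week 12 limit. Under 5.4.1, if the decision falls less than 4 weeks after the last dose, "an Early Withdrawal Visit will be scheduled as soon as is reasonably possible". Protocol 6.10.2 states the same duty only for a need arising before the Week 12 dose, and 4.4 says that "study treatment will be discontinued (if applicable), and the procedures and visits described in Section 5.4 and Table 3 will be performed".
- **Permitted rescue.** Protocol 6.10.2: "After completing the Week 16 visit, or after Early Withdrawal from Treatment, subjects may use prohibited concomitant medications for the treatment of worsening AD".
- **Completion.** Protocol 5.5 counts a subject as having completed study treatment "if he/she receives all planned doses of study treatment through Week 12 and completes the Week 16 visit". Rescue is not mentioned.
- **Non-response, protocol.** Section 9.4.1: "Subjects withdrawing prematurely from the study prior to the Week 16 visit will be assumed to be non-responders".
- **Non-response, SAP.** Section 12.5.3: "a non-responder imputation will be used for all early withdrawal subjects", for visits after withdrawal, in the primary and secondary endpoint tables. The footnotes to the Table 2.1 and 2.3 shells confine it to study withdrawal for lack of efficacy or disease progression.
- **EASI.** SAP 12.5.3 uses observed EASI at each visit. The SAP 12.9.5 display list notes imputation for Tables 2.1 and 2.3 but not for Table 2.6 (EASI-50/75).
- **Visit slotting.** SAP 12.2 drops unscheduled visits. If several assessments fall in one visit interval, "then the latest assessment will be used for summary tables and analyses".
- **Intercurrent events.** SAP 7.1.3, 7.2.3 and 7.3.3 plan no strategy.

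**The concern.** A Week 16 score taken after a course of topical or systemic rescue measures study drug plus rescue. The protocol wants the effect of mepolizumab alone, so such a score should not count as a success, and the plan should say so. It leaves the matter to rules about withdrawal, which is a different event, and gives three versions of the trigger: leaving the study (Protocol 9.4.1), being an early withdrawal subject (SAP 12.5.3), and leaving the study for lack of efficacy or disease progression (the footnotes).

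At stake are the reported Week 16 response rates, their difference and the posterior probabilities, all of which will be read as monotherapy results. The direction is not fixed. A rescued placebo success shrinks the difference, and a rescued mepolizumab success enlarges it. The usual backstop is gone too: SAP 2.1 removes the per-protocol population, and SAP 4.1 only lists protocol deviations.

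**Working it through.** **1. The plan's own figure.** Protocol 9.2.1 and Table 7 give about 80% (0.799) for 25 per arm, true rates 40% and 10%, and success if P(difference ≥ 15 points | data) > 70%. With a flat normal prior on the difference:

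power = Φ[(0.30 − 0.15)/√((0.4×0.6 + 0.1×0.9)/25) − z(0.70)] = Φ(0.15/0.1149 − 0.524) = Φ(0.781) = 0.783.

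This is within 2 points of the stated value, so the criterion is understood. Rescue does not enter it.

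**2. What the text does with each rescued subject at Week 16.**

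- *Last dose at Baseline or Week 4.* Post-Treatment Visit 2 comes 8 weeks after the last dose, at Week 8 or Week 12. There is normally no Week 16 score to count.
- *Last dose at Week 8, procedures followed.* The second post-treatment visit is at 8 + 8 = Week 16, and rescue is allowed meanwhile. IGA: SAP 12.5.3 most naturally imputes non-response, since only subjects who discontinue treatment early have separate post-treatment visits to slot. Read literally, Protocol 9.4.1 and the footnotes do not, because the subject is still in the study; those who do leave are described separately in Protocol 4.2.2: "Subjects who are withdrawn from the study will complete an Early Withdrawal visit and then exit the study". EASI-50/75: the observed post-rescue score counts. No deviation is needed.
- *Rescue after the Week 12 dose, procedures followed.* Early Withdrawal Visit, then Post-Treatment Visit 1 at 12 + 4 = Week 16. IGA: most naturally imputed under 12.5.3. EASI-50/75: observed, and the latest-assessment rule selects the later, post-rescue score if both fall in the Week 16 interval.
- *Rescue after the Week 12 dose, procedures not followed (a deviation).* The subject meets the completer definition. IGA and EASI are both observed.

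The second case shows the inconsistency: one subject, one visit, IGA failure and possibly EASI-75 success.

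**3. Size for IGA.** The documents give neither a rescue rate nor the final sample size. Assumptions: independent Beta(1,1) priors (SAP 7.1.5.1 says only non-informative); few responders (SAP 2.1 refers to limited responders); 14 per arm (half of 56, split 1:1) or 20 per arm (if enrolment continued up to the stop). Each posterior is Beta(1 + x, 1 + n − x), and the posterior mean difference is (x_M − x_P)/(n + 2). P(p_M − p_P ≥ 0.15) was found by numerical integration and checked with 2,000,000 draws.

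| Responders, mepolizumab v placebo | n per arm | P(diff ≥ 15 points) | Mean difference |
|---|---|---|---|
| 1 v 0 | 14 | 0.172 | 1/16 = 6.3 points |
| 2 v 0 | 14 | 0.385 | 2/16 = 12.5 points (80% CrI −0.7 to 27.0) |
| 2 v 1 | 14 | 0.229 | 1/16 = 6.3 points (−9.2 to 22.1) |
| 1 v 0 | 20 | 0.081 | 1/22 = 4.5 points |
| 2 v 0 | 20 | 0.221 | 2/22 = 9.1 points |
| 2 v 1 | 20 | 0.125 | 1/22 = 4.5 points |

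One rescued placebo success (2 v 0 to 2 v 1) lowers the probability by 0.385 − 0.229 = 0.156 at 14 per arm and by 0.221 − 0.125 = 0.096 at 20. One rescued mepolizumab success (1 v 0 to 2 v 0) raises it by 0.385 − 0.172 = 0.213 and by 0.221 − 0.081 = 0.140. All values stay below 0.70. P(mepolizumab rate ≥ 40%) hardly moves: 0.005 to 0.027 at 14 per arm.

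**4. Size for EASI-50/75.** Table 2.6 reports differences in proportions. One subject shifts an arm by 1/14 = 7.1 points or 1/20 = 5.0 points.

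**The case against.** The strongest reply is that the protocol already leads rescued subjects to non-response. Sections 4.2.4 and 5.4.1 require withdrawal from treatment with no Week 12 cut-off, an Early Withdrawal Visit follows when the last dose is under 4 weeks old, and SAP 12.5.3 covers all early withdrawal subjects. This stands for IGA. A reader might infer from the completer definition and the conditional wording in 4.4 that any subject rescued after Week 12 can count as an IGA success under the plan. The documents do not support that: it takes a departure from the withdrawal procedures, or a literal preference for 9.4.1 or the footnotes over 12.5.3. The reply does not settle which of the three triggers governs, and it does not reach EASI-50/75.

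It is also fair that any single reclassified responder has this effect in so small a sample, that EASI-50/75 is exploratory and descriptive, and that affected subjects could be traced through the listings of discontinuations, deviations, concomitant medications, IGA and EASI (Listings 3, 6, 10, 27 and 28). These points limit the weight of the problem. A listing does not correct a summary table.

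A last objection concerns the remedy. Scoring every permanent treatment discontinuation as failure would go too far. Sponsor termination is a listed reason for stopping treatment in 5.4.1, and this study was terminated, so unrescued subjects with a genuine Week 16 success would be recorded as failures. That is right, and the fix below avoids it.

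**Conclusion.** The point holds in a limited form. No explicit rule makes prohibited AD therapy before the Week 16 assessment a non-response. For IGA the fault is an undefined phrase in SAP 12.5.3 that conflicts with Protocol 9.4.1 and the table footnotes, plus an uncovered deviation after the Week 12 dose. For EASI-50/75 the stated rule itself gives the wrong result, with no deviation involved.

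One affected subject moves P(difference ≥ 15 points) by about 0.10 to 0.21, given Beta(1,1) priors, 14 to 20 per arm and one or two mepolizumab responders. These counts are assumptions, and the documents do not show that any such subject exists.

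A reader might infer that the trial's conclusion or its futility stop is in doubt. Neither follows. No illustrated result approaches 0.70, and the stop used Week 8 as its decision point and came before this SAP. At the planned 25 per arm under a flat normal posterior, one extra placebo responder would take 8 v 2 (0.798) to 8 v 3 (0.670) and cross the threshold, but that needs full enrolment and planning-level response, which this study did not have. The harm is to the reported estimates and how they are read. It should be fixed because the correction is cheap.

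**What to change.** Leave access to rescue unchanged and amend the SAP.

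1. In 7.1.3, 7.3.3 and 12.5.3, state that a subject is a non-responder for IGA and EASI-50/75 from the point of use if, after the first dose and before the Week 16 assessment, the subject takes a Table 1 therapy for AD, or a systemic immunosuppressant, systemic glucocorticoid or biologic for any reason. This applies whether or not the subject withdraws and overrides the latest-assessment rule in 12.2. Settle borderline Table 1 items by blinded medical review.
2. Use one further trigger in 12.5.3 and in the Table 2.1 and 2.3 footnotes: withdrawal from the study before Week 16, or treatment discontinuation for worsening AD or lack of efficacy.
3. Do not impute non-response for an unrescued subject whose treatment stopped because the sponsor ended the study and who has an observed Week 16 assessment.
4. Keep observed EASI means in Table 2.4, and flag post-rescue values in Listings 27 and 28.
5. Report the observed-data IGA result beside the main one, because the rule is added after the interim unblinding.

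The cost is SAP wording, one flag from concomitant medication data that Protocol 6.10 already requires, and one extra display. Response rates may be slightly lower, and a single early course of rescue will count as failure at Week 16.
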